	Grade 2	Hold study drug/study regimen dose until resolution to \leq Grade 1 Permanently discontinue study drug/study regimen if it does not resolve to \leq Grade 1 within 30 days or if there are signs of respiratory insufficiency or autonomic instability	Grade 2 - Discuss with the study physician - Care should be taken to monitor patients for sentinel symptoms of a potential decompensation as described above - Obtain a Neurology Consult - Sensory neuropathy/neuropathic pain may be managed by appropriate medications (e.g., gabapentin, duloxetine, etc.) MYASTHENIA GRAVIS 
 o Steroids may be successfully used to treat Myasthenia Gravis. Important to consider that steroid therapy (especially with high doses) may result in transient worsening of myasthenia and should typically be administered in a monitored setting under supervision of a consulting neurologist. o Patients unable to tolerate steroids may be candidates for treatment with plasmapheresis or IVIG. Such decisions are best made in consultation with a neurologist, taking into account the unique needs of each patient. o If Myasthenia Gravis-like neurotoxicity present, consider starting acetylcholine esterase (AChE) inhibitor therapy in addition to steroids. Such therapy, if successful, can also serve to reinforce the diagnosis. GUILLAIN-BARRE: 
 o Important to consider here that the use of steroids as the primary treatment of Guillain-Barre is not typically considered effective.

	Grade of the Event (NCI CTCAE version 4.03)	Dose Modifications	Toxicity Management
			Patients requiring treatment should be started with IVIG and followed by plasmapheresis if not responsive to IVIG.
	Grade 3	Hold study drug/study regimen dose until resolution to \leq Grade 1 Permanently discontinue Study drug/study regimen if Grade 3 irAE does not resolve to \leq Grade 1 within 30 days or if there are signs of respiratory insufficiency or autonomic instability	For severe or life threatening (Grade 3 or 4) events: 
 - Discuss with study physician - Recommend hospitalization - Monitor symptoms and obtain neurological consult MYASTHENIA GRAVIS 
 o Steroids may be successfully used to treat Myasthenia Gravis. It should typically be administered in a monitored setting under supervision of a consulting neurologist. o Patients unable to tolerate steroids may be candidates for treatment with plasmapheresis or IVIG. o If Myasthenia Gravis-like neurotoxicity present, consider starting acetylcholine esterase (AChE) inhibitor therapy in addition to steroids. Such therapy, if successful, can also serve to reinforce the diagnosis. GUILLAIN-BARRE: Important to consider here that the use of steroids as the primary treatment of Guillain-Barre is not typically considered effective. Patients requiring treatment should be started with IVIG and followed by plasmapheresis if not responsive to IVIG
	Grade 4	Permanently discontinue study drug/study regimen	

Infusion-Related Reactions		
Severity Grade of the Event (NCI CTCAE version 4.03)	Dose Modifications	Toxicity Management
Any Grade	General Guidance	
 - Management per institutional standard at the discretion of investigator - Monitor patients for signs and symptoms of infusion-related reactions (e.g., fever and/or shaking chills, flushing and/or itching, alterations in heart rate and blood pressure, dyspnea or chest discomfort, skin rashes etc.) and anaphylaxis (e.g., generalized urticaria, angioedema, wheezing, hypotension, tachycardia, etc.)
Grade 1	The infusion rate of study drug/study regimen may be decreased by 50% or temporarily interrupted until resolution of the event	For Grade 1 or Grade 2: 
 - Acetaminophen and/or antihistamines may be administered per institutional standard at the discretion of the investigator - Consider premedication per institutional standard prior to subsequent doses - Steroids should not be used for routine premedication of <Grade 2 infusion reactions
Grade 2	The infusion rate of study drug/study regimen may be decreased 50% or temporarily interrupted until resolution of the event Subsequent infusions may be given at 50% of the initial infusion rate	
Grade 3/4	Permanently discontinue study drug/study regimen	For Grade 3 or 4: Manage severe infusion-related reactions per institutional standards (e.g., IM epinephrine, followed by IV diphenhydramine and ranitidine, and IV glucocorticoid)

Non-immune Mediated Reactions		
(Note: As applicable, for early phase studies, the following sentence may be added: “Any event greater than or equal to Grade 2, please discuss with Study Physician”)		
CTC Grade/Severity Grade of the Event (NCI CTCAE version 4.03)	Dose Modification	Toxicity Management
Any Grade	Note: dose modifications are not required for adverse events not deemed to be related to study treatment (i.e. events due to underlying disease) or for laboratory abnormalities not deemed to be clinically significant.	Treat accordingly as per institutional standard
1	No dose adjustment	Treat accordingly as per institutional standard
2	Hold study drug/study regimen until resolution to ≤ Grade 1 or baseline	Treat accordingly as per institutional standard
3	Hold study drug/study regimen until resolution to ≤ Grade 1 or baseline For AEs that downgrade to ≤ Grade 2 within 7 days or resolve to ≤ Grade 1 or baseline within 14 days, resume study drug/study regimen administration at next scheduled dose . Otherwise, discontinue study drug/study regimen	Treat accordingly as per institutional standard
4	Discontinue Study drug/study regimen (Note for Grade 4 labs, decision to discontinue would be based on accompanying clinical signs/symptoms and as per Investigator’s clinical judgment and in consultation with the sponsor)	Treat accordingly as per institutional standard

Note: As applicable, for early phase studies, the following sentence may be added: “Any event greater than or equal to Grade 2, please discuss with Study Physician.”

### 3. Revision History

SAP Version 1 was approved prior to the first visit when a subject receives study drug or any other protocol intervention.

## 4. Study Objectives

### 4.1. Primary Objective

#### Dose Escalation

The primary objective of the dose-escalation part of this study is to assess the safety and tolerability of LY2510924 SQ daily in combination with durvalumab by identifying dose-limiting toxicities (DLTs) and the maximum-tolerated dose (MTD) of the combination in patients with advanced (metastatic and/or unresectable) solid tumors.

#### Dose Expansion

The primary objective of the dose-expansion part of this study is to assess the safety of LY2510924 SQ daily in combination with durvalumab in patients with advanced pancreatic and ovarian cancers.

### 4.2. Secondary Objectives

- To characterize the pharmacokinetics (PK) of LY2510924 and durvalumab when co-administered
- To characterize the immunogenicity of durvalumab when administered in combination with LY2510924
- To assess the antitumor activity of the combination of LY2510924 and durvalumab in patients with advanced solid tumors

### 4.3. Exploratory Objectives

The exploratory objective of this study is to examine biomarkers, including pharmacodynamic markers, relevant to LY2510924 and durvalumab, including but not limited to, immune cells/immune functioning, drug targets, cancer-related pathways and the disease state, and to correlate these markers with clinical outcome.

## 5. Summary of Study Design

Study CXAD is a multicenter, nonrandomized, open-label, dose-escalation Phase 1a/1b study of LY2510924 combined with MEDI4736.

This Phase 1a/1b study will be conducted in 2 parts. The first part (Phase 1a) of the study will consist of a dose-escalation assessment of the safety and tolerability of CXCR4 administered with MEDI4736 with advanced refractory solid tumors (Figure CXAD.4.1). The second part (Phase 1b) of the study will be disease restricted to include 2 expansion arms in advanced pancreatic cancer (N=approximately 15 patients) and ovarian cancer (N= approximately 15 patients), all receiving LY2510924 (dose determined from Phase 1a) with MEDI4736.

Dose escalation for LY2510924 in combination with MEDI4736 in Phase 1a will be driven by an adaptive model-based dose-escalation scheme (Neuenschwander et al. 2008) to assist in estimation of DLT rate at recommended dose levels. It provides quantitative guidance on the determination of the dose level and provides a lower underdosing rate and a higher MTD selection rate than traditional 3+3 method. The starting dose level will be 20 mg. Subsequent dose levels will reflect a maximum increment of 10 mg from the prior dose level. If the MTD has not yet been reached at the highest dose level of 40 mg, then additional dose levels may be investigated based on both safety and the available PK data. The dose escalation method is described in details in Attachment 9 of the protocol.

### 5.1. Determination of Sample Size

To determine the MTD of LY2510924, an adequate sample size is required. A sufficient sample size will allow for an accurate evaluation of the relationship between exposure and toxicity, as well as an evaluation of the relationship between exposure and pharmacological effects using descriptive statistics and appropriate modeling techniques, if data warrant.

The actual sample size of the dose escalation (Phase 1a) will primarily be limited by the incidence of DLTs. Under the adaptive scheme, each dose level will enroll 3 patients initially and additional patient cohorts may be enrolled in case of DLT. The anticipated sample size for Phase 1a ranges from approximately 12 to 15 patients, depending on the incidence of DLTs. As shown in protocol Attachment 9, the mean number of patients in simulated trials using this dose escalation method was at most 15 patients. Each expansion arm in Phase 1b will enroll approximately 15 patients. The overall sample size is thus estimated to be approximately 45 patients.

The sample size of 15 patients in Phase 1b has been selected to allow adequate assessment of safety at the recommended dose level. It can provide adequate precision for the estimated incidence rate of the following quantities of interest: (1) patients having a specified AE or (2) patients showing a response (PR/CR) to treatment. Example point estimates of incidence rates and corresponding 2-sided 95% confidence intervals (CI) are summarized in **Error! Reference source not found.** The values are provided as a reference for estimation rather than a basis of any decision criteria. The MTD may be revised based on the safety data obtained in Phase 1b (Iasonos and O'Quigley 2013).

**Table CXAD.5.1. Estimated Incidence Rate and Its Two-sided 95% Confidence Interval**

Num. of Cases (N=15)	Est. Rate	95% CI a	
		Lower Limit	Upper Limit
0	0.0	0.0	0.22
3	0.2	0.04	0.48
6	0.4	0.16	0.68
9	0.6	0.32	0.84

[figure not shown]
Abbreviations: CI = confidence interval; Est. = estimated; N = number of patients.

a 95% Clopper-Pearson interval for binomial distribution with sample size of 15

## 5.2. Method of Assignment to Treatment

This study is open-label for Phase 1a and Phase 1b. Before each patient's enrollment into the study, an eligibility check must be conducted between the investigational site and the Lilly clinical research personnel to confirm that each patient meets all enrollment criteria. Upon confirmation of eligibility, the sponsor will confirm the dose and identification number assignment and cohort/expansion arm for each patient.

For Phase 1a, if investigators have eligible patients who have consented concurrently, more than 3 patients may be entered at a particular dose level provided that accrual has not ceased due to excessive toxicity. This enrollment procedure is allowed because of the advanced disease state of this patient population and the screening involved in defining eligibility. This event should be approved by the sponsor following discussions with the investigators.

Abbreviations: approx. = approximately; I/E = inclusion/exclusion criteria; IV = intravenous; LY = LY2510924; Ph1a = Phase 1a; PK/PD = pharmacokinetic/pharmacodynamic; pts = patients; MTD = maximum-tolerated dose; SQ = subcutaneous.

**Figure CXAD.4.1. CXAD study design.**

## 6. A Priori Statistical Methods

### 6.1. General Considerations

Statistical analysis of this study will be the responsibility of Eli Lilly and Company. The interpretation of the study results will be the responsibility of the investigator with the Lilly CRP/CRS, pharmacokineticist, and statistician. The CRP/CRS and statistician will also be responsible for the appropriate conduct of an internal review for both the final study report and any study-related material to be authorized by Lilly for publication.

The analyses for this study will be descriptive; no p-values will be calculated. Data analyses will be provided by cohort and overall whenever appropriate. For continuous variables, summary statistics will include number of patients, mean, median, standard deviation, standard error, minimum, and maximum. Categorical endpoints will be summarized using number of patients, frequency, percentages, and their standard errors. Exploratory analyses of the data that are not described in the protocol will be conducted as deemed appropriate.

Any change to the data analysis methods described in the protocol will require an amendment ONLY if it changes a principal feature of the protocol. Any other change to the data analysis methods described in the protocol and the justification for making the change will be described in the clinical study report (CSR).

The following data handling conventions will be used in the analysis (see [Table CXAD.6.1](#) **Error! Reference source not found.**).

**Table CXAD.6.1. Data Handling Conventions**

Term	Definition or Rule
Relative Study Day	
If assessment is on or after date of first dose then  <math>(\text{date of assessment}) - (\text{date of first study drug dose}) + 1</math>
 
If assessment precedes first dose of drug then  <math>(\text{date of assessment}) - (\text{date of first study drug dose})</math>
 
There is no Study Day 0. Study Day 1 is the date of first dose and study day -1 is the day before the first dose.

Baseline	
For change from baseline analyses, baseline value is defined as the last reported measure on or before the first dose date (prior to the dose administration), unless otherwise specified.
 
For change from baseline within a cycle, baseline value is defined as the measure prior to the first dose of that cycle, unless otherwise specified.
 
If more than one pre-dose measure is available, they may be averaged if appropriate.

Entered	Patients who have signed the informed consent form directly or through their legally acceptable representatives.
Enrolled	Patients who have been assigned to a study treatment and have received at least one dose of study treatment.

## 6.2. Handling of Dropouts or Missing Data

Missing data, except dates, will not be imputed. Historical data such as historical diagnosis, historical illness, pre-existing conditions and prior therapies should be collected in a sufficiently informative way. For example, in order to be considered as a historical illness, events occurring in the same year as study entry should have at least known month and year for the end date, while events occurring in previous years should have at least a known year for the end date; all previous treatments for cancer should have at least known date, month, and year for the end date, in order to determine if inclusion criteria is met. When dates need to be imputed, missing days will be replaced with 15th of the month and missing day/month with 01 JULY.

Patients who withdraw from the study before receiving study drug will be replaced and will not be included in the safety or efficacy assessments unless the withdrawal is due to a safety issue that is possibly related to study procedure.

In the following situations, patients will be considered DLT-evaluable; otherwise, patients are considered DLT nonevaluable and may be replaced to ensure that enough patients complete one cycle of therapy at each dose level, unless accrual to that cohort has stopped due to a DLT:

1. Completed the DLT observation period (Cycle 1) and received the scheduled durvalumab dose and at least 75% of LY2510924 doses in Cycle 1;
2. discontinued study treatment or study participation before completing Cycle 1 due to a DLT.

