The combination of CXCR4 inhibitor with anti-PD-L1 immunotherapy has shown increased infiltration of T cells into tumors and tumor regression in an in vivo pancreatic cancer mouse model (Feig et al. 2013). This study will investigate the effects of CXCR4 inhibition (LY2510924) in combination with PD-L1 inhibition (durvalumab).

This study is a Phase 1a/1b open-label study that will be conducted in 2 parts. The Phase 1a portion of this study will consist of a dose assessment of the safety and tolerability of LY2510924 administered at 20, 30, or 40 mg subcutaneously (SQ) daily in combination with durvalumab 1500 mg intravenously (IV) once every 28 days in patients with advanced refractory solid tumors. The LY2510924 dose in the Phase 1b portion of this study will be based on Phase 1a results. The Phase 1b portion will include expansion arms in 2 indications, pancreatic and ovarian cancer (N=15 each arm). Enrollment will be complete when the expansion arms

have reached the prespecified enrollment target. Safety and efficacy analysis of each expansion arm will be performed independently of the other arm.

Clinical Protocol Synopsis: Study I2V-MC-CXAD

Name of Investigational Product: LY2510924 and durvalumab (MEDI4736)	
Title of Study: A Phase 1a/1b Study of CXCR4 Peptide Antagonist (LY2510924) Administered in Combination with the Anti-PD-L1 Antibody, Durvalumab (MEDI4736), in Advanced Refractory Solid Tumors	
Number of Planned Patients: Phase 1a: approximately 12-15 patients Phase 1b: approximately 30 patients	Phase of Development: 1a/1b
Length of Study: Approximately 2 years Planned first patient visit: August 2016 Planned last patient visit: August 2018	

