### 6.8.3. Adverse Events

AE terms and severity grades will be assigned by the investigator using CTCAE Version 4.0. Any minor version of CTCAE Version 4.0 (for example, CTCAE Version 4.03) may be used for this study. In addition, AE verbatim text will also be mapped by the sponsor or designee to corresponding terminology within the Medical Dictionary for Regulatory Activities (MedDRA) dictionary. AEs will be reported using a unified CTCAE/MedDRA reporting process:

- The CTCAE v4.0 term reported by the investigator will be mapped to the MedDRA preferred term (PT) and system organ class (SOC) of the corresponding MedDRA lowest level term (LLT), unless the reported CTCAE term is “Other-specify”.

- If the reported CTCAE term is “Other-specify” the MedDRA LLT, PT and SOC mapped from the verbatim AE term will be used
- All listings and summaries will use the CTCAE terms when available or the MedDRA LLT, along with the MedDRA PT resulting from this process.

A treatment emergent adverse event (TEAE) is defined as any AE that begins on or after the day of the first dose of study treatment or any pre-existing condition that increases in CTCAE grade on or after the day of the first dose of study treatment, and prior to the end of the short-term (safety) follow-up. Comparisons of pre-existing conditions to treatment events at the LLT level will be used in the treatment-emergent computation.

The number of patients who experienced a TEAE, SAE, or TEAE possibly related to study drug, will be summarized. TEAEs will be summarized by SOC, by PT terms of decreasing frequency within SOC, and by maximum CTCAE grade and “Any grade” categories. Immune-related AEs may be tabulated if deemed appropriate.

Historical illnesses are defined as events which ended before completion of the screening visit. Pre-existing conditions are defined as AEs that begin but do not resolve prior to the first dose of study drug is administered. The pre-existing conditions will be presented by patient and can be combined with the adverse event listing, so that the history of the pre-existing conditions/adverse events can be traced. Historical illnesses and pre-existing conditions will be summarized and listed by cohort and overall for all patients on therapy.

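### SAP 6.2 imputes partial dates with no bound at first dose, so adverse events with partial onset dates can be wrongly classed as treatment-emergent or not, in either direction

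*SAP*

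**What the plan says.** SAP 6.2 opens with a general statement: "Missing data, except dates, will not be imputed". It then discusses how complete historical diagnoses, illnesses and prior therapies should be, and closes with the imputation rule: "When dates need to be imputed, missing days will be replaced with 15"th of the month, and "missing day/month with 01 JULY". No variable is exempted, and there is no lower or upper bound. Neither document gives another rule for adverse event or death dates.

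SAP 6.8.3 defines a TEAE by date, as "any AE that begins on or after the day of the first dose of study treatment", with a second limb for "any pre-existing condition that increases in CTCAE grade on or after the day of the first dose of study treatment". It adds: "Pre-existing conditions are defined as AEs that begin but do not resolve prior to the first dose of study drug is administered". The incidence tables rest on this flag: "TEAEs will be summarized by SOC, by PT terms of decreasing frequency within SOC". SAP 6.17 also requires TEAE status for the registry table of 'Other' (non-serious) events.

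Protocol 8.1 makes safety the primary endpoint, measured by adverse events, serious adverse events, deaths and laboratory abnormalities. The protocol synopsis gives "Planned first patient visit: August 2016".

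**The concern.** Adverse events are collected from consent (Protocol 8.1.2.2.1), and screening lasts up to 28 days (Protocol 6.2.2). Events just before and just after the first dose are therefore both in the database, and onset date is the main thing that separates them. A mid-month or mid-year rule that ignores the first dose can put an event on the wrong side of that line even when the known parts of the date are compatible with onset on treatment.

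An on-treatment event moved before first dose and still unresolved at first dose becomes a pre-existing condition. It drops out of the tables by system organ class, preferred term and grade, and out of the registry 'Other' table. A screening event moved the other way is counted as toxicity. With about 15 patients per expansion arm, a single patient is visible in a reported rate.

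**Working it through.** **The plan's own figures.** The SAP's incidence table for N=15 uses exact Clopper-Pearson limits. For 0 cases the upper limit is 1 − 0.025^(1/15) = 0.218. Beta quantiles give 0.043–0.481 for 3 cases, 0.163–0.677 for 6 and 0.323–0.837 for 9. All agree with the table after rounding. The documents give no figure for date imputation.

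**Single cases under the SAP rules.**
- First dose 20 Sep 2016, onset 25 Sep, day missing: imputed to 15 Sep, 5 days before first dose. Not a TEAE; wrong.
- First dose 20 Sep, onset 5 Oct, day missing: imputed to 15 Oct. TEAE; right. Only onset in the same calendar month as first dose is at risk.
- First dose 10 Sep, screening event 5 Sep, day missing: imputed to 15 Sep. TEAE; wrong.
- First dose Aug–Dec 2016, onset on treatment, only 2016 known: imputed to 01 Jul 2016. Not a TEAE; wrong.
- First dose March 2017, pre-dose event, only 2017 known: imputed to 01 Jul 2017. TEAE; wrong.

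**Event rates.** Assumptions, not from the documents: one first dose on each day from 1 Aug 2016 to 31 Jul 2017 (365 days: seven 31-day months, four 30-day months and one 28-day month), and onset equally likely on each study day considered.

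*Patients who could be affected.* First-dose days after the 15th number 7×16 + 4×15 + 13 = 185, and 185/365 = 51%. This counts patients at risk, not events lost.

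*Day missing, onset on study days 1–28.* A start on day d > 15 of a month of length L loses the L − d + 1 onset days left in that month. Summed over d this is (L−15)(L−14)/2, which is 136, 120 or 91 for L = 31, 30 or 28. The total is 7×136 + 4×120 + 91 = 1523, out of 365×28 = 10,220: **14.9%**.

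*Day missing, onset in the first 7 days.* The same sum with each term capped at 7 gives 91, 84 and 70. The total is 7×91 + 4×84 + 70 = 1043, out of 365×7 = 2555: **40.8%**.

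*Reverse error, day missing, onset in the 28 days before first dose.* A start on day d ≤ 15 pulls in the d − 1 earlier days of that month. The sum of d − 1 for d = 1 to 15 is 105; 12×105 = 1260, and 1260/10,220 = **12.3%**.

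*Year only, Cycle 1 onset.* For starts from 1 Aug to 31 Dec 2016 there are 153×28 = 4284 start–onset pairs. Of these, 1 + 2 + … + 27 = 378 fall in January 2017 and are classed correctly. The other 3906 (**91%**) are placed before first dose. Over the full year of starts, those first dosed on 2–31 July 2017 add 30×28 = 840, giving 4746/10,220 = 46%.

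**Effect on a rate.** One patient in 15 is 1/15 = 6.7 percentage points. Losing one changes 3/15 = 0.20 (0.04–0.48) to 2/15 = 0.13 (0.02–0.40), or 1/15 = 0.07 (0.00–0.32) to 0/15 (0.00–0.22).

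**The case against.** The best defence is that the imputation sentence ends a passage on historical data, applies only when a date needs imputing, and is never said to govern event onset. That does not rescue it. The wording is general, the section begins with all missing data, and nothing else in either document covers event or death dates. If the rule were historical only, those dates would have no rule, and the same addition would be needed.

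Other parts of the defence stand:
- On-treatment events are graded at Cycle 1 Days 1 and 15 and at each later cycle, and the CRF data are reviewed with computer edits (Protocol 9.1). Partial dates should be uncommon, and year-only onsets rarer still.
- A misdated unresolved event remains in the pre-existing-condition listing, which may be combined with the adverse event listing, and returns as a TEAE if its grade rises.
- The study is descriptive, and a 6.7-point shift is small beside an interval such as 0.04–0.48.

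A reader might go further and infer that the rule consistently understates toxicity on the primary outcome. The documents do not support that. The error runs both ways. The Phase 1a primary objective concerns DLTs and the MTD, and DLTs are summarised for the safety population without a TEAE condition (SAP 6.8.2). Serious events are counted separately from TEAEs and, in the registry table, regardless of TEAE status. Deaths have their own summaries, and laboratory grades come from the measured values. A reader might also take the 51% of patients dosed after the 15th as a share of events lost, or suppose that every event dated only 2016 is wrongly classed. Neither follows: the event share is about 15% of day-missing Cycle 1 events, and true screening events dated only 2016 are classed correctly.

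**Conclusion.** The point holds as a two-way misclassification. Applied as written, SAP 6.2 and 6.8.3 together give a wrong answer for identifiable cases; this is a stated rule with a faulty result, not just missing detail. Among day-missing events, about 15% of Cycle 1 onsets and 41% of first-week onsets are lost from the TEAE tables, and about 12% of onsets in the 28 days before first dose are wrongly added. Year-only 2016 onsets on treatment in patients starting August to December 2016 are always placed before first dose.

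These percentages are conditional on a date being partial and rest on evenly spread first doses and onsets. The documents do not give the frequency of partial dates, so the expected number of affected patients cannot be calculated; it is probably small. The consequence falls mainly on non-serious events, in the TEAE tables and the registry 'Other' table, and matters most in the 15-patient expansion arms.

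The same unbounded rule can place an imputed death date before the patient was last known alive. That touches overall survival and the split of deaths around 30 days after discontinuation (SAP 6.8.4). No size is claimed for it. The change should be made before database lock.

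**What to change.** Keep the 15th and 01 July for historical data. Add to SAP 6.2:

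- For adverse event onset, if month and year are known and both equal those of the first dose, or only the year is known and equals the first-dose year, impute the first-dose date, unless the end date shows that the event ended before first dose.
- If the known parts show onset before first dose, the event stays pre-dose. Both month and year must match in the first rule; otherwise an onset known to be in January 2017 could be moved to a March 2017 first dose.
- An imputed death date is never earlier than the day after the patient was last known alive.

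Under this rule none of the on-treatment losses calculated above remain. The price is more of the opposite error: every day-missing screening event in the first-dose month counts as treatment-emergent unless its end date rules it out. On the same assumptions, summing min(28, d − 1) over start days gives 462, 434 or 378 for months of 31, 30 or 28 days. The total is 7×462 + 4×434 + 378 = 5348, and 5348/10,220 = 52% of day-missing events in the 28 days before first dose, before end dates are used, against 12% now. With few partial dates this should be a handful of events at most, and it is the conservative direction for safety. Flagging imputed onsets in the listing would let a reader see them. The cost is a few sentences in the SAP and a programming rule; no extra data are needed.
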